The Judith Jaffe Multiple Sclerosis Center currently has over 1000 patients in a clinical and MRI database. Patients who have signed consent for the database will have their standard of care MRI scans monitored for new enhancing lesions; this will only have to be repeated if initial scan is not completed at our MS center with our current clinical protocol. All RRMS patients with new enhancing lesions will be considered for the study and approached regarding participation. Patients that are considered candidates and consent for the study, patients will then be randomized (1:1) to receive one course of ACTH followed by monthly pulses vs. receiving only one course of ACTH treatment. All patients will have follow-up MRI's at 3 months, 6 months and 12 months post lesion onset for a total of 3 additional scans. If a patient is identified as having an enhancing lesion from MRI scan not obtained through our database, an additional scan will be obtained through the study and serve as the baseline MRI. All patients will receive the first course of ACTH within 4 weeks of new lesion detection.

3.2: Study endpoints

The primary endpoint of this study will be change in MWF within new enhancing lesions over the course of 12 months. The absolute change in lesion MWF (over our test-retest variability) between baseline and one year MRI's will be calculated and compared between treatment groups.

The main secondary end-point will be longitudinal assessment of MWF (every 3 months) to determine the dynamics of myelin change over 12 months, specifically to determine the timing of remyelination. The advantage of T2 relaxometry is the ability to look at both the contribution of water within myelin bilayers (MWF) but also the water within the intra/extracellular compartment (the intermediate peak within the T2 spectrum). This second peak (extracellular peak) can increase with edema, thus once the extracellular pool stabilizes, we can ensure that any change in myelin water fraction (MWF) is a true reflection of myelination.

We will also explore a measurement called “absolute myelin content”. Through this measurement, we can control for the increased edema associated with a new lesion, thus providing for a more accurate measure of true myelin change.

Additional secondary end points include measurement of the following clinical measurements: EDSS, and the following MRI measurements: change in T2 lesion volume, whole brain volume, and cortical volume.

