Baseline visit: Baseline EDSS (if not obtained during screening visit), *consent signed*, schedule repeat MRI with and without contrast if screening MRI not completed as part of the Weill Cornell Multiple Sclerosis Center Clinical Protocol. Initiation of ACTH (H.P. Acthar®) course of therapy following visit (patient will do home therapy) after randomization.

Visit 1: EDSS, safety evaluations, and initiation of monthly course of ACTH (H.P. Acthar®) in patients randomized to this arm.

Visit 2: EDSS, safety evaluations.

Visits 3, 4, 5: EDSS, safety evaluations, MRI with and without contrast

Visit 6 (last visit): EDSS, safety evaluations, MRI with and without contrast.

3.7 Study schema:

Tests and Evaluations	Time point: screening/ Baseline	Visit 1 (1 month)	Visit 2 (2 months)	Visit 3 (3 months)	Visit 4 (6 months)	Visit 5 (9 months)	Visit 6 (12 months- end of study)
Consent obtained	X						
MS history and EDSS, safety evaluations	X	X	X	X	X	X	X
Randomization to treatment arm	X						
MRI	X			X	X	X	X

4 Assessment and documentation of adverse events

An AE is any physical or clinical worsening in symptoms or disease experienced by the patient at any time during the course of the study, whether or not it is considered related to study participation

or procedures. Multiple sclerosis symptoms that worsen during the course of the trial will be treated as AEs. AEs may also include complications that occur as a result of protocol-mandated procedures.

ACTH Safety Background

ACTH has been approved by the US Food and Drug Administration for treatment of MS relapses, however, we are proposing to use this drug on a monthly pulsed dosing (80mg for three days per month) schedule for one year. A few trials have evaluated the longer-term clinical benefit and safety profile of ACTH pulse therapy in idiopathic glomerular diseases, such as nephrotic syndrome and focal segmental glomerulosclerosis (FSGS), as well as one pilot study in MS. These studies had varying dosing schedules, some of which included a higher per month drug exposure as compared to our proposed study [26-30]. None of the studies reported severe-events related to ACTH and the adverse events were consistent with the expected common side effect profile listed on approved label. Based upon these studies, the adverse events between the two groups of patients proposed in this study should be similar.

The studies are summarized below.

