Use of H.P. Acthar Gel may be associated with central nervous system effects ranging from euphoria, insomnia, irritability, mood swings, personality changed, severe depression and psychosis. Existing emotional instability or psychotic tendencies may be aggravated.

Patients with a comorbid disease may have that disease worsened. Symptoms of diabetes and myasthenia gravis may be worsened with treatment.

Prolonged use of H.P. Acthar Gel may produce posterior subcapsular cataracts, glaucoma with possible damage to the optic nerves and may enhance the establishment of secondary ocular infections due to fungi and viruses.

H.P. Acthar Gel is immunogenic. Prolonged administration of H.P. Acthar Gel may increase the risk of hypersensitivity reactions. Neutralizing antibodies with chronic administration may lead to a loss of endogenous ACTH activity.

There is an enhanced effect in patients with hypothyroidism and in those with cirrhosis of the liver.

Decrease in bone formation and an increase in bone resorption both through an effect on calcium regulation and inhibition of osteoblast function may occur. These, together with a decrease in the protein matrix of the bone (secondary to an increase in protein catabolism) and reduced sex hormone production, may lead to the development of osteoporosis. Bone density should be monitored in patients on long term therapy.

H.P. Acthar Gel has been shown to have an embryocidal effect. Women of child-bearing potential should use approved methods of birth-control while administering the drug.

3. Adverse Reactions after Additional Postmarketing Experience

A. The following adverse reactions associated with the use of H.P. Acthar Gel have been identified from the postmarketing experience with H.P. Acthar Gel.

Allergic responses have presented as dizziness, nausea and shock.

Necrotizing angitis and congestive heart failure.

Skin thinning, facial erythema and increased sweating.

Pancreatitis, abdominal distention and ulcerative esophagitis.

Headache, vertigo, subdural hematoma, intracranial hemorrhage.

The adverse event collection period for this study begins at the baseline visit and will end after the last day of study medication. Patients discontinued from the study will be followed for at least 14 days after the last day of the study medication. At each visit patients will be specifically asked for adverse events using the table below.

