All AEs, the onset and resolution dates, relationship to study drug, severity and seriousness will be documented. Based on the available information, the physician investigator will use the following guidelines to determine the relationship of any adverse event to the use of the study drug:

Unrelated: No temporal association, or the cause has been identified, or study medication cannot be implicated

Possible: Temporal association, but other etiologies are likely to be the cause; however, involvement of study medication cannot be excluded

Probable: Temporal association, other etiologies are possible, but unlikely.

The severity of adverse events experienced during the course of the study will be assessed using a grading system:

Grade 1: Mild; asymptomatic or mild symptoms; clinical or diagnostic observations only; intervention not indicated.

Grade 2: Moderate; minimal, local or noninvasive intervention indicated; limiting age-appropriate instrumental activities of daily living.

Grade 3: Severe or medically significant but not immediately life-threatening AE; hospitalization or prolongation of hospitalization indicated; disabling; limiting self-care activities of daily living.

Grade 4: Life-threatening consequences; urgent intervention indicated.

Grade 5: Death related to AE

Reference: Common Terminology Criteria for Adverse Events (NIH):

http://evs.nci.nih.gov/ftp1/CTCAE/CTCAE_4.03_2010-06-14_QuickReference_5x7.pdf

Adverse events that occur during the study (from enrollment through the final visit), regardless of treatment group or relationship to the research, will be reported according to the policy of WCMC's Office of Research Integrity and Assurance and Data Safety Monitoring Board.

As per WCMC IRB reporting policy, only AE Grades 3, 4, and 5 will be reported to the IRB and DSMB.

(http://weill.cornell.edu/research/rea_com/irb_adv.html

All safety data will be reported to the WCMC DSMB. No efficacy interim analysis will be performed. Safety review will be done by the DSMB after the six-month visit of the first patient and then yearly. More frequent meetings or meetings ad-hoc could be organized if needed or

requested by the DSMB. The study does not have preset rules for discontinuation. Upon review of the data, the DSMB can recommend stopping the study at any time if appropriate.

5. References

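### Section 4 ends adverse-event collection at the last dose; if the initial ACTH course counts as study medication, this closes Group A's window before Visit 1 and contradicts the protocol's other adverse-event rules

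*Protocol*

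**What the plan says.** One sentence in Section 4 defines the collection period: "The adverse event collection period for this study begins at the baseline visit and will end after the last day of study medication". Four other statements bear on the same period, and none distinguishes the arms:

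- Section 4, definition of an adverse event: any worsening "experienced by the patient at any time during the course of the study".
- Section 4, shortly after the collection-period sentence: "At each visit patients will be specifically asked for adverse events using the table below".
- Section 4, reporting rule: "Adverse events that occur during the study (from enrollment through the final visit), regardless of treatment group or relationship to the research" are to be reported.
- Sections 3.6 and 3.7: safety evaluations are scheduled at baseline and at months 1, 2, 3, 6, 9 and 12. The last entry reads "Visit 6 (last visit): EDSS, safety evaluations, MRI with and without contrast".

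Section 3.1 fixes treatment by arm. Both arms receive the same initial course, typically 3-5 days and adjustable up to 2-3 weeks. Group A then receives nothing further, and Group B receives a 3-day pulse each month for 12 months. Section 3.6 starts the pulses at Visit 1 (month 1). Section 3.1 also describes the initial course as standard of care, and the protocol does not say whether it counts as study medication.

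**The concern.** The last day of study medication comes at very different times in the two arms because that is what is being randomized. A collection window tied to it is therefore unequal by design, while every other statement on adverse events describes a window that is the same for both.

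A concrete case shows the conflict. Section 4 treats worsening MS symptoms as adverse events. A Group A patient who worsens at month 6 has an adverse event under the definition and the reporting rule. On the reading that the initial course is study medication, that event falls outside the stated collection period.

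If sites followed the sentence, Group A would be observed for days to weeks and Group B for about a year. Crude counts by arm would then reflect length of observation as well as treatment, and the DSMB reviews safety without preset discontinuation rules. An analysis plan could not repair this, because events that were never collected cannot be recovered.

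**Working it through.** The protocol gives no figure to reproduce; the check is day arithmetic on its own durations.

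**Inputs**
- Initial course: 3-5 days, up to 14-21 days (Section 3.1).
- Pulses: 3 days monthly, first pulse at Visit 1 (Sections 3.1 and 3.6).
- Post-baseline visits: months 1, 2, 3, 6, 9, 12 (Section 3.7).
- Month = 365.25/12 = 30.44 days, so Visit 1 is at about day 30 and Visit 6 at about day 365.
- Assumption 1: the initial course is study medication.
- Assumption 2: it starts at about baseline. Section 3.6 places it directly after that visit: "course of therapy following visit (patient will do home therapy) after randomization".

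**Group A.** Last dose = length of the initial course.
- Typical course: day 3 to 5, or 3/365.25 = 0.8% to 5/365.25 = 1.4% of the year.
- Extended course: day 14 to 21, or 14/365.25 = 3.8% to 21/365.25 = 5.7%.
- Visit 1 is at day 30, so 0 of 6 post-baseline visits fall inside.

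**Group B.** Last dose = (month of last pulse × 30.44) + 3.
- Last pulse at month 11 (11 pulses): 11 × 30.44 + 3 = 338; 5 of 6 visits inside.
- Last pulse at month 12 (12 pulses): 12 × 30.44 + 3 = 368; 6 of 6 visits inside.

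**Ratio of windows, B to A**
- 21-day initial course: 338/21 = 16 to 368/21 = 18.
- 5-day initial course: 338/5 = 68 to 368/5 = 74.

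These are ratios of observation time, not of event counts.

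**Under the reporting rule and the visit schedule:** about 365 days and 6 of 6 visits in each arm.

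**If Assumption 1 fails,** Group A has no study medication, the sentence gives it no end date, and no ratio can be formed.

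**On Assumption 2.** Section 3.1 allows some latitude: "All patients will receive the first course of ACTH within 4 weeks of new lesion detection". That clock runs from lesion detection, not from baseline. Both arms receive the same initial course, and Group B's pulses follow it from Visit 1, so the design implies that the course is over by then. A start late enough to carry it past Visit 1 would have pulses beginning before the course had ended. No figures are therefore given for such a start.

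**The case against.** The strongest reply is that the protocol largely settles the matter itself. The definition, the instruction to ask at each visit, the reporting rule and the visit schedule all point to equal windows, and a site following the schedule would question both arms at every visit. The unequal-window scenario needs one sentence to override four. This stands, and it limits the severity. It does not remove the defect, because that sentence is the only one that expressly defines the collection period.

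A second reply is that the reporting rule concerns reporting, not collection. That is true, but an event has to be collected before it can be reported, and the visit-level instructions lead to the same place independently.

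A third reply is that the sentence says collection ends after the last day of medication without saying how long after, or that it refers to the study as a whole. The wording leaves some room, but prompt closure is the natural reading, and the next sentence is written per patient.

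Two stronger readings are tempting and do not hold:

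- A reader might infer that the rules conflict for Group A however study medication is understood. They do not. If the standard-of-care initial course is excluded, the sentence is silent on Group A, and the reporting rule fills the gap.
- A reader might also count the follow-up rule as a further contradiction: "Patients discontinued from the study will be followed for at least 14 days after the last day of the study medication". A Group A patient removed for a relapse months after the initial course has already passed 14 days. But the rule sets a minimum, and a patient beyond a minimum contradicts nothing.

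**Conclusion.** The contradiction is real on the reading that the initial course is study medication. With a start at about baseline, Group A's window closes by about day 3 to 21, before any post-baseline visit, against about day 338 to 368 in Group B. On the other reading there is a gap, not a contradiction.

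The consequence is confined to descriptive safety data: by-arm counts reaching the DSMB would not be comparable if the sentence were followed. A reader might infer that a planned safety comparison is biased. The protocol does not support that. It names no safety endpoint and no between-arm safety test, and its remark in Section 4 that adverse events should be similar in the two groups is an expectation only. Confidence in the wording conflict is high. Whether unequal windows would arise in practice is uncertain, since most of the text points the other way. Severity: minor to should-fix.

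**What to change.** Replace the collection-period sentence in Section 4 with:

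> AEs are collected in both arms, regardless of treatment group, from the baseline visit through the final visit (Visit 6), or until the patient leaves the study if earlier.

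Keep the existing 14-day follow-up of discontinued patients as an additional minimum, and state whether the initial ACTH course counts as study medication.

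If a Group B pulse can fall after Visit 6, as the month-12 calculation allows, the pulse schedule in Section 3.1 and the last visit in Section 3.6 must be reconciled; this review takes no position on how.

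The cost is one replaced sentence and one clarification. No visits are added, because safety evaluations at Visits 1-6 are already scheduled in both arms.

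### Section 4 of the Protocol ends adverse-event collection with the last dose, which conflicts with its own study-long safety schedule and would give the two arms very unequal observation if followed

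*Protocol*

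**What the plan says.** Section 4 (Assessment and documentation of adverse events) sets the collection rule: "The adverse event collection period for this study begins at the baseline visit and will end after the last day of study medication". The next sentence makes one extension, for one set of patients only: "Patients discontinued from the study will be followed for at least 14 days after the last day of the study medication".

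Other statements point to a longer window, the same in both arms:

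- Section 4 defines an adverse event as a worsening "experienced by the patient at any time during the course of the study, whether or not it is considered related to study participation".
- Section 4, straight after the two sentences above: "At each visit patients will be specifically asked for adverse events using the table below".
- Section 4, on reporting: "Adverse events that occur during the study (from enrollment through the final visit), regardless of treatment group". It adds: "All safety data will be reported to the WCMC DSMB".
- Sections 3.6 and 3.7 list safety evaluations at baseline and at Visits 1 to 6 (months 1, 2, 3, 6, 9 and 12), with no restriction by arm.

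On dosing, Section 3.1 gives both groups an initial course, usually 3 to 5 days and at most 2 to 3 weeks. Only Group B then receives a 3-day pulse each month for 12 months, and Section 3.6 starts these pulses at Visit 1.

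**The concern.** A collection window tied to the last dose is harmless when both arms stop dosing at about the same time. Here they do not: Group A finishes after one short course, while Group B is dosed for about a year. The arm that serves as the safety comparator would drop out of observation almost at once.

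Three features of the trial make this matter. First, Section 4 expects adverse events to be similar in the two groups, and the trial could not check that without follow-up in Group A. Second, Section 4 counts worsening MS symptoms as adverse events. Under the sentence as written, such worsening would be recorded through the year in Group B and for most of the year not in Group A, so raw counts would tilt against Group B at equal underlying rates. Third, the DSMB has no preset stopping rules and judges the accumulated data, so it depends on both arms being collected alike.

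Dividing by observed time would not repair the comparison, because Group A would have no observed time after its initial course. Section 4 also names adrenal insufficiency after withdrawal as a risk, and a window that closes with the last dose leaves out the period in which that would appear.

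**Working it through.** The Protocol states no length in days for the collection period, so there is no figure to reproduce. The check is day arithmetic on the sentence as written, followed by a comparison with the other statements.

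**Inputs**

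- Initial course: 3–5 days usually, 21 days at most (Section 3.1).
- Lag from baseline visit to first dose: not stated. Section 3.1 says "All patients will receive the first course of ACTH within 4 weeks of new lesion detection". That clock starts at lesion detection, so 0 to 28 days from the baseline visit is an assumption, and 28 is generous.
- Monthly pulses: 3 days each, starting at month 1. The month of the last pulse is not fixed; month 11 and month 12 both fit the wording.
- One month = 365/12 = 30.4 days.

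**Group A, not discontinued: window = lag + course**

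| Lag (days) | Course (days) | Window (days) |
|---|---|---|
| 0 | 3 | 3 |
| 0 | 5 | 5 |
| 0 | 21 | 21 |
| 28 | 5 | 33 |
| 28 | 21 | 49 |

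For a discontinued patient, the minimum 14-day follow-up takes the last row to 49 + 14 = 63 days.

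**Group B, pulses completed: window = month of last pulse × 30.4 + 3**

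- Last pulse at month 11: 11 × 30.4 + 3 = 337 days.
- Last pulse at month 12: 12 × 30.4 + 3 = 368 days.
- If monthly means every 28 to 30 days, the range is 11 × 28 + 3 = 311 to 12 × 30 + 3 = 363 days.

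**Comparison**

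- Ratio of observation time, longest Group A window against month-11 Group B window: 337/49 = 6.9. With no lag and a 21-day course: 337/21 = 16. With no lag and a 5-day course: 337/5 = 67.
- Share of a 365-day study observed: Group A at most 49/365 = 13%; Group B at least 337/365 = 92%.
- At an illustrative equal rate of one event per patient-year, the expected recorded events per patient are at most 0.13 in Group A and at least 0.92 in Group B.
- Scheduled safety visits inside the window: a 49-day window reaches Visit 1 (about day 30) but not Visit 2 (about day 61). A 337-day window covers Visits 1 to 5.

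**Against the other statements**

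The study-long definition, the questioning at each visit, the reporting window and the visit schedule all give about 365 days for a completer in either arm, a ratio of about 1 to 1. The reporting statement and the collection sentence concern different steps, but that does not reconcile them: an event that is not collected cannot be reported. No text says which rule prevails.

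**The case against.** The strongest reply is that the Protocol largely answers itself. Patients are asked about adverse events at each visit, every visit to month 12 carries a safety evaluation in both arms, and reporting covers the whole study. Staff would have to set all of that aside to produce the imbalance. This stands as a limit on the consequence. A reader might infer that safety data will in fact be lost in Group A, or that what reaches the DSMB will be biased. The documents do not support that; it happens only if the collection sentence is followed over the rest.

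Two readings of the sentence soften it. Ending after the last dose need not mean ending on that day, and Visit 6 is also after Group A's last dose. But that reading leaves no usable end date. Alternatively, study medication might mean only the randomised pulses, since Section 3.1 treats the initial course as standard of care. Group A then has no last day of study medication, and its window is undefined. Neither reading removes the conflict, though the second means that the Group A day counts hold only if the initial course counts.

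The day counts are also not strict bounds for every patient. Discontinued Group A patients could reach 63 days, and Group B patients removed for relapse (Section 3.2) would have less than 337. Section 3.2 lists no safety endpoint, and the Protocol describes no between-arm test of adverse events.

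Finally, because the month of the last pulse is open, a reader might infer that it should be set at month 11 to leave about four weeks before Visit 6. The documents do not support that as a correction. Section 3.1 specifies 12 months of treatment, twelve pulses is at least as natural a reading, and fixing month 11 could remove a pulse from the regimen. That is a separate dosing decision.

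**Conclusion.** The point holds as an internal contradiction that should be corrected. The collection sentence in Section 4 cannot be squared with the definition, the reporting window and the visit schedule. If it were followed, Group A would be observed for days to about 7 weeks and Group B for about 11 to 12 months, and adverse events could not be compared fairly between arms.

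That size rests on four assumptions: the initial course counts as study medication; Group A patients are not discontinued; Group B patients complete their pulses; and, for the 7-week upper end, a 4-week lag is followed by a 3-week course. The usual 3–5 day course would make the Group A window shorter. The other statements suggest that collection to month 12 in both arms was probably intended, so the fault lies in one sentence and not in the design of safety follow-up.

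**What to change.** Replace the collection sentence in Section 4 with:

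*Adverse events are collected in both arms from the baseline visit through the final visit (Visit 6) or, for discontinued patients, until at least 14 days after the last dose if later.*

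The cost is wording only. Safety evaluations are already scheduled for all patients to month 12, so no visit is added in either arm.

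Optional: if the last pulse falls at month 12, completers in Group B would have no scheduled observation after it, whereas discontinued patients get at least 14 days. One telephone safety contact at least 14 days after that pulse would close the gap. With 15 patients per arm (Section 3.5), that is at most about 15 calls and about two weeks' longer follow-up for those patients.
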